7.2 STUDY ASSESSMENT AND TREATMENT SCHEDULE - TREATMENT FREE OBSERVATION

Cycle = 28 days	Treatment-Free Observation (TFO) Visits ¹	
Procedures/Days ²	TFO1 Cycle 1 Day 1	TFO Subsequent Day 1 Every 3 Cycles for 24 cycles and every 6 cycles thereafter
ECOG	X	X
Physical Examination	X	X
Vital Signs ³	X	X
Hematology	X	X
Chemistry	X	X
PB MRD ⁴		X
AE Evaluation	X	X
Con Meds	X	X

¹ At completion of 24 cycles with no progression of disease (POD), confirmed U-MRD, or discontinuation of treatment due to toxicity in absence of POD, subjects will enter a treatment-free observation period. Study assessments will be completed every 3 cycles for 24 cycles from discontinuation of any study drug.

² All TFO visits have a +/- 14 day window.

³ Vital signs to include temp, BP, HR, and respirations

⁴ Subjects on treatment-free observation with U-MRD should have peripheral blood MRD assessments approximately every 12 weeks +/- 2 weeks prior to Cycle 24 and every 24 weeks +/- 2 weeks, unless clinically indicated sooner, after Cycle 24. For subjects entering treatment-free observation with D-MRD, no PB MRD is required. For subjects entering TFO due to discontinuation of treatment due to toxicity in absence of POD, MRD should be done at TFO1. If U-MRD repeat MRD in PB in 4 weeks, if D-MRD, no further PB MRD is required.

7.3 STUDY ASSESSMENT AND TREATMENT SCHEDULE – RE-TREATMENT

Cycle=28 days	Screen	Cycle 1 ¹				Cycle 2 ²		Cycle 3 ³				Cycles 4-8 ⁴		C11-C26 ⁵	EOS ⁶	LTFU
Procedures/Days	D-28 to D1	D1	D8 ⁶	D15 ⁷	D22 ⁷	D1	D8 ⁷	D1	D2	D8	D15	D1	D1 every 3 Cycles			
Physical Examination	X	X				X		X				X	X	X		
ECOG PS	X	X				X		X				X	X	X		
Vital Signs ⁸	X	X	X	X	X	X	X	X	X	X	X	X	X	X		
12-Lead EKG	X															
Hematology	X	X	X	X	X	X	X	X	X	X	X	X	X	X	X	
Chemistry	X	X	X	X	X	X	X	X	X	X	X	X	X	X	X	
Coagulation Studies	X	X				X		X					X	X		
HCV, HBV, CMV ⁹	X															
CMV surveillance ¹⁰								X				C6&8	C11, 14, 17 etc			
MRD-PB ¹¹	X											X ²⁶	X ²⁶			
β ₂ -microglobulin	X															
Pregnancy Test ¹³	X					X		X				X	X			
Response Assessments ¹⁴	X											C7	X ¹⁵		X ¹⁶	
Tumor Lysis Risk Assessment ¹⁷		X														
AE Assessment	X	X	X	X	X	X	X	X	X	X	X	X	X	X	X	
Con Meds	X	X	X	X	X	X	X	X	X	X	X	X	X	X	X	
Ublituximab ¹⁸								X	X	X	X	X	X	X	X	
Umbralisib ¹⁹												Daily until confirmed U-MRD				
Cohort A: Ibrutinib ²⁰												Daily until confirmed U-MRD				
Cohort B: Venetoclax ²¹												Dose ramp-up as per package insert and daily until confirmed U-MRD				
Cohort C: Acalabrutinib												Every 12 hours until confirmed U-MRD				

¹ Treatment Administration +/- 1 day window after cycle 1 day 1. Physical Exam, Vital Signs, ECOG PS, Hematology and Serum Chemistry visit days have - 1 day window. All assessments must be completed prior to treatment.

² Treatment Administration +/- 3 day window. Physical Exam, Vital Signs, ECOG PS, Hematology and Serum Chemistry visit days have a - 3 day window during Cycles 2 through 6.

³ Treatment Administration +/- 7 day window. Physical Exam, Vital Signs, ECOG PS, Hematology and Serum Chemistry visit days have a - 7 day window.

⁴ Treatment Administration +/- 3 day window. Physical Exam, Vital Signs, ECOG PS, Hematology and Serum Chemistry visit days have a - 3 day window during Cycles 2 through 6.

⁵ Day 1 every 3 Cycles (Cycle 11, 14, 17, 20, 23, 26): Treatment Administration +/- 7 day window. Physical Exam, Vital Signs, ECOG PS, Hematology and Serum Chemistry visit days have a - 7 day window.

⁶ Cycle 1 Days 8, 15 & 22 assessments only for subjects receiving venetoclax.

⁷ Cycle 2 Day 8 assessments only for subjects receiving venetoclax.

⁸ Vital signs to include temp, BP, HR, respirations and weight (weight only at baseline).

⁹ Serum Virology to include HBsAg, HBC antibody, HCV antibody, CMV IgG and CMV IgM or CMV by PCR. If HBC antibody is positive, the subject must be evaluated for the presence of HBV DNA by PCR - See Appendix D. If the subject is CMV IgG or CMV IgM positive, the subject must be evaluated for the presence of CMV DNA by PCR.

¹⁰ CMV surveillance by PCR every 3 cycles while receiving study treatment. In addition, a final CMV test by PCR should be done upon treatment discontinuation if not already done within previous 3 months.

¹¹ For retreatment, MRD analysis should be done within 30 days of restarting therapy in peripheral blood (PB) then performed Cycles 6, 8, 11, 14, 17, 20, 23, and 26. If U-MRD in PB during retreatment repeat approximately 4 weeks later. If U-MRD confirmed approximately 4 weeks later, discontinue treatment and follow for progression and survival for 24 months.

¹³ For women of childbearing potential: Serum pregnancy test within 3 days prior to Cycle 1/Day 1; Urine pregnancy tests on Day 1 of each treatment cycle +/- 7 days.

¹⁴ Radiology assessment should include contrasted CT or MRI imaging of neck, chest, abdomen, and pelvis. Scans to be completed within 30 days prior to Cycle 1/Day 1.

¹⁵ Re-treatment subjects – radiology and response assessment within 14 days of Cycles 7, 14, 20, 26 then every 12 months thereafter. At the time of response assessment, bone marrow to be performed as per standard of care if other criteria for complete remission are met. CR should only be confirmed once by bone marrow assessment at planned response assessments.

¹⁶ Response Assessment to be done as per SOC to determine progression-free survival

¹⁷ For subjects being re-treated with venetoclax only. Refer to section 8.3.5.1

¹⁸ Ublituximab Cycle 3 Days 1,2, 8 & 15; Cycle 4-8 Day 1 then every 3 cycles (C11, C14, C17, C20, C23, C26). No further ublituximab after cycle 26

¹⁹ When starting retreatment, dose of umbralisib is at the investigator's discretion, previously tolerated dose should be considered.

²⁰ When starting retreatment, dose of ibrutinib or acalabrutinib is at the investigator's discretion, previously tolerated dose should be considered.

²¹ TLS risk assessment and TLS prophylaxis should be instituted per the venetoclax package insert for subjects on Cohort B. Refer to section 7.3.4.1 for additional lab requirements during the ramp up phase. Dose escalation should be performed per the package insert and the target dose may be 400 mg or previously tolerated dose.

***EOS = End of Study** – EOS visit occurs if subject is discontinuing from the study. Please see Section 5.6 Discontinuation from study , which outlines reasons subject could discontinue from study.

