7 STUDY ASSESSMENTS AND TREATMENT SCHEDULES

7.1 STUDY ASSESSMENT AND TREATMENT SCHEDULE - INITIAL TREATMENT

Cycle=28 days	Screen	Cycle 1 ¹				Cycle 2-6 ²	C9 and every 3 cycles through C24 ³	EOS*
Procedure/Days	-28-1	D1	D2	D8	D15	Day 1	Day 1	
Medical History	X							
Rai Staging	X							
ECOG	X	X				X	X	X
Physical Examination	X	X				X	X	X
Vital Signs⁴	X	X	X	X	X	X	X	X
12-Lead EKG	X							
Hematology	X	X	X	X	X	X	X	X
Chemistry	X	X	X	X	X	X	X	
Coagulation Studies	X	X				X	X	
HCV, HBV, CMV⁵	X							
CMV surveillance⁶						C3&6	C9, 12, 15, etc.	
PB MRD⁷	X					X	X	
β₂-microglobulin	X							
Pregnancy Test⁸	X					X	X	
Response assessments¹⁰	X					C3 & C6	C 12, 18 & C24	
AE Evaluation	X	X	X	X	X	X	X	X
Con Meds	X	X	X	X	X	X	X	X
Ublituximab		X	X	X	X	X	X	
Umbralisib						Daily until confirmed U-MRD ¹¹		
Cohort A: Ibrutinib						Daily until confirmed U-MRD ¹¹		
Cohort B: Venetoclax						Daily until confirmed U-MRD ¹¹		
Cohort C: Acalabrutinib						Every 12 hours until confirmed U-MRD ¹¹		

¹ Treatment Administration +/- 1 day window after cycle 1 day 1. Physical Exam, Vital Signs, ECOG PS, Hematology and Serum Chemistry visit days have - 1 day window. All assessments must be completed prior to dosing.

² Treatment Administration +/- 3 day window. Physical Exam, Vital Signs, ECOG PS, Hematology and Serum Chemistry visit days have a - 3 day window during Cycles 2 through 6.

³ Treatment Administration +/- 7 day window. Physical Exam, Vital Signs, ECOG PS, Hematology and Serum Chemistry visit days have a - 7 day window for all cycles after cycle 6

⁴ Vital signs to include temp, BP, HR, respirations and weight (weight only at baseline).

⁵ Serum Virology to include HBsAg, HBc antibody, HCV antibody, CMV IgG and IgM. If HBc antibody is positive, the subject must be evaluated for the presence of HBV DNA by PCR - See Appendix D. If the subject is CMV IgG or IgM positive, the subject must be evaluated for the presence of CMV DNA by PCR. If subject is HCV positive, evaluate HCV RNA.

⁶ CMV surveillance by PCR every 3 cycles while receiving study treatment. In addition, a final CMV test by PCR should be done upon treatment discontinuation if not already done within previous 3 months.

⁷ For initial treatment, MRD analysis (central lab) in peripheral blood (PB) performed within 30 days prior to Cycle 1/Day 1. MRD analysis in PB during cycles 3, 6, 9, 12, 15, 18, 21, and 24. U-MRD in PB during initial treatment must be confirmed in PB 4 approximately weeks later.

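### Re-treatment Cycle 3 repeats the ublituximab loading of initial Cycle 1 under a ±7 day dosing window instead of ±1 day, and Table 7.3 states two conflicting exam and lab windows for it

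*Combined protocol and SAP*

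**What the plan says.** Section 7.1 (initial treatment) attaches footnote 1 to Cycle 1, with visits on Days 1, 2, 8 and 15. The dosing rule is "Treatment Administration +/- 1 day window after cycle 1 day 1". Exam, vital signs, ECOG, hematology and chemistry have a −1 day window, and "All assessments must be completed prior to dosing".

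Section 7.3 (re-treatment) delays ublituximab and umbralisib until Cycle 3. Footnote 18 gives the infusion days: "Ublituximab Cycle 3 Days 1,2, 8 & 15; Cycle 4-8 Day 1 then every 3 cycles". The Cycle 3 column (Days 1, 2, 8 and 15) carries footnote 3: "Treatment Administration +/- 7 day window. Physical Exam, Vital Signs, ECOG PS, Hematology and Serum Chemistry visit days have a - 7 day window". Footnote 3 does not say that assessments come before treatment.

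That requirement does appear in Table 7.3, in footnote 1 ("All assessments must be completed prior to treatment"). Footnote 1 belongs to re-treatment Cycle 1, where no ublituximab is scheduled.

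Footnotes 2 and 4 of the same table, attached to Cycle 2 and to Cycles 4–8, both end: "Hematology and Serum Chemistry visit days have a - 3 day window during Cycles 2 through 6". That range includes Cycle 3.

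**The concern.** The protocol otherwise treats re-treatment Cycle 3 as the counterpart of initial Cycle 1. Section 8.3.1.1 (stopped infusions), Section 8.3.1.2 (flow rates) and Section 8.3.1.3.1 (dilutions) each pair the two cycles explicitly. Only the visit windows were not carried across.

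Elsewhere in the two treatment schedules, a ±7 day dosing window is used only for infusions three cycles apart: Table 7.1 footnote 3 ("Hematology and Serum Chemistry visit days have a - 7 day window for all cycles after cycle 6") and Table 7.3 footnote 5 ("Day 1 every 3 Cycles (Cycle 11, 14, 17, 20, 23, 26): Treatment Administration +/- 7 day window"). In Cycle 3 it is applied to doses one week apart or less.

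What is at stake is the timing of the loading doses and of the counts taken before them. Table 2 (Section 8.4.1) delays ublituximab for Grade 4 neutropenia or thrombocytopenia, and that rule is only as current as the count it uses. The protocol's own background shows that cytopenia is a practical matter: Section 2.2.2 reports Grade 3/4 neutropenia in 67% of 12 CLL subjects on weekly ublituximab (150 mg, then 450 mg), and Section 9.5.2.1 reports 41% (98/240) with venetoclax.

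**Working it through.** No power or sample-size figure is involved. The check compares the footnotes and works out the days they allow.

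**1. Are the two cycles the same loading?** Section 8.1 gives initial Cycle 1 as 150 mg (Day 1), 750 mg (Day 2) and 900 mg (Days 8 and 15). Section 8.2 gives re-treatment Cycle 3 the same doses on the same days for Cohorts A, B and C. The synopsis re-treatment table shows Cohort C loading in Cycle 1, but Sections 5.4 and 8.2 and footnote 18 put it in Cycle 3.

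**2. Does footnote 3 belong to Cycle 3?** Markers 1 to 5 run in column order across the table, and 3 falls on the Cycle 3 column. The other four footnotes name their own cycles: 1; 2 through 6 (twice); and 11 to 26.

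**3. Allowed dosing days** (nominal day ± window, counting Day 0):

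| Dose | Re-treatment Cycle 3, ±7 | Initial Cycle 1 rule, ±1 |
|---|---|---|
| Day 2 | 2−7 to 2+7 = −5 to 9 | 1 to 3 |
| Day 8 | 8−7 to 8+7 = 1 to 15 | 7 to 9 |
| Day 15 | 15−7 to 15+7 = 8 to 22 | 14 to 16 |

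Under ±7, the Day 2 and Day 8 windows overlap on Days 1–9, and the Day 8 and Day 15 windows overlap on Days 8–15. Keeping the doses in order, the Day 8 to Day 15 gap can run from 0 to 22−1 = 21 days with both doses in window. Under ±1 these windows do not overlap, and the gap runs from 14−9 = 5 to 16−7 = 9 days.

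**4. Earliest in-window draw for the Day 15 count:**

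- Footnote 3: 15−7 = Day 8, the nominal day of the preceding 900 mg infusion.
- Footnotes 2 and 4, read literally: 15−3 = Day 12.
- Initial Cycle 1 rule: 15−1 = Day 14.

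Table 7.3 thus gives two answers for exam and labs in Cycle 3, and both are looser than the initial rule. The −3 day wording concerns exam and lab visits; it does not displace the ±7 day dosing window in footnote 3.

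**The case against.** **The lab window is not plainly −7 days.** This stands. A reader of footnote 3 alone might infer that the protocol settles on counts up to a week old. The document does not support that, because footnotes 2 and 4 give −3 days over a range that includes Cycle 3. The accurate statement is that the lab window is contradictory; the ±7 day dosing window is the firm part.

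**The safety consequence is limited.** This also stands. Hematology and chemistry are scheduled separately on Cycle 3 Days 1, 2, 8 and 15. Section 8.4 requires a clinical toxicity assessment at each visit, and the Table 2 delay rule still applies. Nothing shows that an old count would be relied on, and a scheduling tolerance is not permission to merge two 900 mg infusions. What remains is that the table would not class such timing as out of window, and the other safeguards do not fix when the count is taken.

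**Window as a share of the dosing interval.** A reader might try to show that Cycle 3 is unique on this scale, since Day 8 to Day 15 gives 7/7 = 100%. That does not hold. The initial Cycle 1 rule gives 1/1 = 100% for Day 1 to Day 2 and 1/6 = 17% for Day 2 to Day 8, and initial Cycle 1 Day 15 to Cycle 2 Day 1 gives 3/14 = 21%. The sound comparison is 7 days against 1 day for the same doses.

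**It may be deliberate, or the superscript may be misread.** Re-treated subjects have already received ublituximab on study, so a looser rule is conceivable, but no rationale is given. Numbering carried over from Table 7.1 is a plausible cause; that is inference. Some superscripts in Table 7.3 are unreliable as read. If marker 3 did not belong to Cycle 3, the loading cycle would have no dosing window of its own and would still need one.

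**Conclusion.** The point holds and should be corrected. As written, re-treatment Cycle 3 has a ±7 day dosing window where the identical initial loading has ±1 day, and the Day 8 and Day 15 windows overlap. Its exam and lab window is stated as both −7 and −3 days, against −1 day initially. The assessments-first rule is missing from the loading cycle and sits instead on a cycle without ublituximab.

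The reach is narrow: safety and conduct in one cycle, among subjects who progress after 6 months of treatment-free observation and are re-treated. The documents do not say how many are expected. A reader might infer an effect on the primary result; there is none, because the primary U-MRD rate in Section 11.6.1.1 is assessed during initial treatment.

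The conclusion rests on footnote 3 belonging to the Cycle 3 column and, for Cohort C, on Sections 5.4 and 8.2 taking precedence over the synopsis table.

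**What to change.** Replace footnote 3 of Table 7.3 with a rule for the loading cycle:

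- Dosing: ±3 days for Cycle 3 Day 1; ±1 day for Days 2, 8 and 15, counted from the actual Cycle 3 Day 1.
- Physical exam, vital signs, ECOG, hematology and chemistry: −1 day, completed before that day's dose.

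Cycle 3 Day 1 needs its own tolerance. Unlike initial Cycle 1 Day 1, it is not time zero but follows two cycles of the oral agent; ±3 days matches the adjacent cycles. Limiting the assessments-first rule to the listed items avoids a clash with footnote 13, which allows the Day 1 urine pregnancy test ±7 days.

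Correct the cycle range at the end of footnote 2 to Cycle 2 only, and at the end of footnote 4 to Cycles 4 through 8. This removes the conflicting −3 day reference to Cycle 3 and gives Cycles 7 and 8 a stated lab window.

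The cost is three footnote edits in one table at the next amendment, slightly less scheduling flexibility in one re-treatment cycle, and possibly an extra blood draw at a visit already scheduled.

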7.4 LABORATORY ASSESSMENTS

Laboratory assessments will be collected as specified in the study assessments and treatment schedules. Please refer to the lab manual for instructions outlining collection and shipment procedures for lab samples for central review.

7.4.1 LOCAL LABORATORY ASSESSMENTS

1. Hematologic profile and serum chemistry to include:

Hematologic Profile		
Hematocrit	Neutrophils	Platelet count
Hemoglobin	Lymphocytes	Absolute lymphocyte count
Erythrocyte count	Monocytes	
Leukocyte count	Eosinophils	
Absolute neutrophil count	Basophils	

Serum Chemistry		
Albumin	Creatinine	SGOT [AST]
Alkaline phosphatase	Glucose	SGPT [ALT]
Bicarbonate/CO ₂	LDH	Sodium
BUN	Magnesium	Total bilirubin
Calcium	Phosphorus	Total protein
Chloride	Potassium	Uric acid

2. Serum pregnancy test.
3. Coagulation lab tests to include PT and INR.
4. Beta2-microglobulin
5. Serum virology to include HBsAG, HBc antibody, HCV antibody, and CMV IgG and IgM or CMV by PCR during screening, then CMV by PCR at subsequent timepoints. If HBc antibody is positive the subject must be evaluated for the presence of active HBV DNA by PCR (see Appendix D). If the subject is CMV IgG or IgM positive, the subject must be evaluated for the presence of CMV DNA by PCR.
6. Bone Marrow biopsy and aspiration for subject that meet the criteria for CR as defined by iwCLL Hallek 2018.

7.5 CENTRAL LABORATORY ASSESSMENTS

The following assessments will be shipped to and analyzed at a central laboratory. Please see Lab Manual for details of processing, handling, and shipping instructions.

- Peripheral Blood Minimal Residual Disease (MRD) Analysis (use CLL MRD specimen shipping kits, see lab manual)

8 TREATMENT PLAN

8.1 TREATMENT SUMMARY

Initial Treatment Overview Cycle = 28 days

Cohort A: Ublituximab and Umbralisib with Ibrutinib

Cycle 1:

Ublituximab			Umbralisib	Ibrutinib
Day 1	Day 2	Day 8 & 15	Daily	Daily
150 mg	750 mg	900 mg	800 mg	previously tolerated dose

Cycles 2 through 6:

Ublituximab	Umbralisib	Ibrutinib
Day 1	Daily	Daily
900 mg	800 mg	previously tolerated dose

Cycles 7-24:

Ublituximab	Umbralisib	Ibrutinib
Day 1 of Cycles 9, 12, 15, 18, 21 & 24	Daily	Daily
900 mg	800 mg	previously tolerated dose

Cohort B: Ublituximab and Umbralisib with Venetoclax

Cycle 1:

Ublituximab			Umbralisib	Venetoclax
Day 1	Day 2	Day 8 & 15	Daily	Daily
150 mg	750 mg	900 mg	800 mg	previously tolerated dose

Cycles 2 through 6:

Ublituximab	Umbralisib	Venetoclax
Day 1	Daily	Daily
900 mg	800 mg	previously tolerated dose

Cycle 7-24:

Ublituximab	Umbralisib	Venetoclax
Day 1 of Cycle 9, 12, 15, 18, 21 & 24	Daily	Daily
900 mg	800 mg	previously tolerated dose

Cohort C: Ublituximab and Umbralisib with Acalabrutinib

Cycle 1:

Ublituximab			Umbralisib	Acalabrutinib
Day 1	Day 2	Day 8 & 15	Daily	Every 12 hours
150 mg	750 mg	900 mg	800 mg	previously tolerated dose

Cycles 2 through 6:

Ublituximab	Umbralisib	Acalabrutinib
Day 1	Daily	Every 12 hours
900 mg	800 mg	previously tolerated dose

UTX-TGR-208

Version 2.0 Dated: 30 July 2020

Cycles 7-24:

Ublituximab	Umbralisib	Acalabrutinib
Day 1 of Cycles 9, 12, 15, 18, 21 and 24	Daily	Every 12 hours
900 mg	800 mg	previously tolerated dose

8.2 RE-TREATMENT SUMMARY

Re-treatment Overview Cycle = 28 Days

Cohort A: Ublituximab and Umbralisib with Ibrutinib (Re-Treatment)

Cycles 1 and 2:

Ibrutinib	
Daily	
Daily at previously tolerated dose. Investigator discretion may be used to start subjects at a higher dose than last tolerated (maximum dose 420mg daily).	

Cycle 3:

Ublituximab			Ibrutinib	Umbralisib
Day 1	Day 2	Day 8 & 15	Daily	Daily
150 mg	750 mg	900 mg	At appropriate dose based on initial protocol treatment.	Previously tolerated dose. Investigator discretion may be used to start subjects at a higher dose than last tolerated (maximum dose 800mg daily).

Cycles 4 through 8:

Ublituximab	Ibrutinib	Umbralisib
Day 1	Daily	Daily
900mg	At appropriate dose based on previous Cycle	At appropriate dose based on previous Cycle

Cycles 9 through 26:

Ublituximab	Ibrutinib	Umbralisib
Day 1 of Cycle 11, 14, 17, 20, 23, 26	Daily	Daily
900 mg	At appropriate dose based on previous Cycle	At appropriate dose based on previous Cycle

Cohort B: Ublituximab and Umbralisib with Venetoclax (Re-treatment)

Cycle = 28 days

Cycle 1:

Venetoclax	
Day 1-28	
Dose escalation per package insert to previously tolerated dose. Investigator discretion may be used to escalate subjects to a target dose that is higher than the dose last tolerated (maximum dose 400mg daily).	

Cycle 2:

Venetoclax	
Day 1-7	Day 8-28
Dose escalation per package insert to previously tolerated dose, if applicable. Investigator discretion may be used to escalate subjects to a target dose that is higher than the dose last tolerated (maximum dose 400mg daily).	Tolerated dose per dose escalation

Cycle 3:

Ublituximab			Venetoclax	Umbralisib
Day 1	Day 2	Day 8 & 15	Daily	Daily
150mg	750 mg	900 mg	At appropriate dose based on previous Cycle	Previously tolerated dose. Investigator discretion may be used to start subjects at a higher dose than last tolerated (maximum dose 800mg daily).

Cycles 4 through 8:

Ublituximab	Venetoclax	Umbralisib
Day 1	Daily	Daily
900 mg	At appropriate dose based on previous Cycle	At appropriate dose based on previous Cycle

Cycles 9 through 26:

Ublituximab	Venetoclax	Umbralisib
Day 1 of Cycle 11, 14, 17, 20, 23 & 26	Daily	Daily
900 mg	At appropriate dose based on previous Cycle	At appropriate dose based on previous Cycle

Cohort C: Ublituximab and Umbralisib with Acalabrutinib (Re-Treatment)**Cycle 1-2:**

Acalabrutinib		
Every 12 hours		
previously tolerated dose		

Cycle 3:

Ublituximab			Acalabrutinib	Umbralisib
Day 1	Day 2	Day 8 & 15	Every 12 hours	Daily

UTX-TGR-208

Version 2.0 Dated: 30 July 2020

150 mg	750 mg	900 mg	At appropriate dose based on initial protocol treatment.	Previously tolerated dose. Investigator discretion may be used to start subjects at a higher dose than last tolerated (maximum dose 800mg daily).
--------	--------	--------	--	---

Cycles 4 through 8:

Ublituximab	Umbralisib	Acalabrutinib
Day 1	Daily	Every 12 hours
900 mg	800 mg	previously tolerated dose

Cycles 9-26:

Ublituximab	Umbralisib	Acalabrutinib
Day 1 of Cycles 11, 14, 17, 20, 23 & 26	Daily	Every 12 hours
900 mg	800 mg	previously tolerated dose

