Cycle 1:

Ublituximab			Umbralisib	Acalabrutinib
Day 1	Day 2	Day 8 & 15	Daily	Every 12 hours
150 mg	750 mg	900 mg	800 mg	previously tolerated dose

[figure not shown]
Cycles 2 through 6:

Ublituximab	Umbralisib	Acalabrutinib
Day 1	Daily	Every 12 hours
900 mg	800 mg	previously tolerated dose

Cycles 7-24:

Ublituximab	Umbralisib	Acalabrutinib
Day 1 of Cycles 9, 12, 15, 18, 21 and 24	Daily	Every 12 hours
900 mg	800 mg	previously tolerated dose

Study Schema - Re-Treatment

*Progression Of Disease (PD) – Defined per the iwCLL Criteria (Hallek 2018)

U2 – ublituximab and umbralisib; IB – ibrutinib; ACALA – Acalabrutinib; VEN – venetoclax; MRD – minimal residual disease; EOS – end of study

Retreatment will start with 2 cycles of single agent treatment with ibrutinib, acalabrutinib or venetoclax per the subject's history on study. Umbralisib and ublituximab will be started in Cycle 3 of re-treatment. Subjects will again be evaluated with serial peripheral blood MRD analysis. If subjects achieve U-MRD status in the peripheral blood, MRD will again be assessed by peripheral blood 4 weeks later to confirm U-MRD. Retreatment will continue until the occurrence of confirmed U-MRD response in the peripheral blood, completion of 26 cycles (24 cycles of triplet therapy), definitive disease progression, unacceptable toxicity, or withdrawal from the study due to investigator decision or other reasons. Subjects who discontinue study treatment and have not progressed will continue to be followed for disease progression.

Re-treatment schedule as follows:

Cohort A: Ublituximab and Umbralisib with Ibrutinib

Cycles 1 and 2:

Ibrutinib				
Daily				
Daily at previously tolerated dose. Investigator discretion may be used to start subjects at a higher dose than last tolerated (maximum dose 420mg daily).				

Cycle 3:

Ublituximab			Ibrutinib	Umbralisib
Day 1	Day 2	Day 8 & 15	Daily	Daily
150 mg	750 mg	900 mg	At appropriate dose based on initial protocol treatment	Previously tolerated dose. Investigator discretion may be used to start subjects at a higher dose than last tolerated (maximum dose 800mg daily).

Cycles 4 through 8:

Ublituximab	Ibrutinib	Umbralisib
Day 1	Daily	Daily
900mg	At appropriate dose based on previous Cycle	At appropriate dose based on previous Cycle

Cycle 9 through Cycle 26:

Ublituximab	Ibrutinib	Umbralisib
Day 1 of Cycle 11, 14, 17, 20, 23 & 26	Daily	Daily
900 mg	At appropriate dose based on previous Cycle	At appropriate dose based on previous Cycle

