5.4 RETREATMENT PHASE

Study Schema for Re-Treatment

*Progression Of Disease (PD) – Defined per the iwCLL Criteria (Hallek 2018)
U2 – ublituximab and umbralisib; IB – ibrutinib; ACALA – Acalabrutinib; VEN – venetoclax; MRD – minimal residual disease; EOS – end of study

Subject on treatment-free observation who subsequently develop clinical progression requiring treatment per iwCLL criteria (Hallek, et al., 2018) after 6 months of treatment-free observation will be retreated with the triple combination regimen that was previously received. Subjects who progress within 6 months of treatment-free observation discontinue from the study.

For subjects enrolled in Cohort A, retreatment will consist of 2 cycles of ibrutinib followed by treatment with ublituximab and umbralisib with ibrutinib cycles 3 through 26 of retreatment. The previously tolerated ibrutinib dose should be considered but is at investigator discretion (maximum dose 420mg daily).

For subjects enrolled in Cohort B, venetoclax should be initiated per the package insert. The target ramp-up dose should be considered based on the previously tolerated dose but is at investigator discretion (maximum dose 400mg daily). Retreatment will consist of 2 cycles of venetoclax followed by treatment with ublituximab and umbralisib with venetoclax cycles 3 through 26.

For subjects enrolled in Cohort C, retreatment will consist of 2 cycles of acalabrutinib followed by treatment with ublituximab and umbralisib and acalabrutinib cycles 3 through 26 of retreatment. The previously tolerated acalabrutinib dose should be considered but is at the investigator discretion.

Clinical response and U-MRD rate will be studied upon retreatment. If subjects achieve U-MRD status in the peripheral blood, MRD will be assessed by peripheral blood 4 weeks later to confirm U-MRD. Retreatment will continue until the occurrence of confirmed U-MRD response in the peripheral blood, completion of 26 cycles (24 cycles of triplet therapy), UTX-TGR-208

Version 2.0 Dated: 30 July 2020

definitive disease progression, unacceptable toxicity, or withdrawal from the study due to investigator decision or other reasons. Subjects who discontinue study treatment and have not progressed will continue to be followed for disease progression.

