Grade ≥3	
Withhold umbralisib until Grade ≤2.
 
If recurrence after re-challenge, delay umbralisib until Grade ≤ 2; thereafter resume umbralisib at current dose or at next lower dose level at discretion of the investigator.

TABLE 4: STUDY DRUG DOSE LEVELS

Study Drug	Starting Dose	1 st Dose Reduction	2 nd Dose Reduction
Umbralisib	800 mg	600 mg	400 mg

A maximum of two dose level reductions are allowed for umbralisib. If a subject requires a dose reduction of umbralisib due to study drug related toxicity, the dose may not be re-escalated. If further evaluation of the toxicity reveals the event was not related to umbralisib, this must be recorded in the medical record and dose re-escalation to the next higher dose level may be considered at the discretion of the investigator.

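### Cohort C re-treatment dosing tables contradict the rest of the protocol: Section 8.2 prints a flat umbralisib 800 mg from Cycle 4, and the synopsis tables repeat the initial-treatment schedule

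*Combined protocol and SAP*

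**What the plan says.** Section 8.2, re-treatment Cycle 3, gives the same umbralisib instruction in all three cohorts: "Previously tolerated dose. Investigator discretion may be used to start subjects at a higher dose than last tolerated (maximum dose 800mg daily". For Cycles 4-8 and 9-26, the Cohort A and B umbralisib cells read "At appropriate dose based on previous Cycle". The Cohort C dose row for the same two blocks (ublituximab, umbralisib, acalabrutinib) reads "900 mg 800 mg previously tolerated dose".

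Section 8.4.2, under Table 4, states: "If a subject requires a dose reduction of umbralisib due to study drug related toxicity, the dose may not be re-escalated". Its one exception is an event later found unrelated to umbralisib. In that case a move up to the next level may be considered.

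On the schedule, the synopsis text says "Retreatment will start with 2 cycles of single agent treatment with ibrutinib, acalabrutinib or venetoclax", with umbralisib and ublituximab added in Cycle 3. Section 5.4 repeats this for Cohort C: "For subjects enrolled in Cohort C, retreatment will consist of 2 cycles of acalabrutinib followed by treatment with ublituximab and umbralisib and acalabrutinib". It also sets the limit: "Retreatment will continue until the occurrence of confirmed U-MRD response in the peripheral blood, completion of 26 cycles (24 cycles of triplet therapy". The synopsis tables for Cohort C re-treatment instead show all three drugs from Cycle 1, in blocks 1, 2-6 and 7-24, with umbralisib 800 mg throughout.

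**The concern.** These are the tables from which a site doses. In 8.2 the Cohort C cells for Cycles 4-26 ignore the individual dose set in Cycle 3. The subjects for whom this matters are those already taken below 800 mg. Table 3 in 8.4.2 requires a lower level after any colitis and after Grade 3 or higher liver toxicity, for example. For such a subject the dosing table says 800 mg and the dose-modification section says no increase. The protocol does not say which prevails.

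A site working from the synopsis would also omit the acalabrutinib lead-in and start the triplet two cycles early. It would then be out of step with instructions tied to re-treatment Cycle 3: prophylaxis start (8.3.2), handling of an interrupted first infusion (8.3.1.1) and infusion rates (8.3.1.2).

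**Working it through.** There is no statistical figure in the plan to reproduce. The check is a comparison of tables plus simple dose and calendar arithmetic.

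**1. Umbralisib cells in 8.2, re-treatment**

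| Cohort | Cycle 3 | Cycles 4-8 | Cycles 9-26 |
|---|---|---|---|
| A | individual, maximum 800 mg | carried forward | carried forward |
| B | individual, maximum 800 mg | carried forward | carried forward |
| C | individual, maximum 800 mg | 800 mg | 800 mg |

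Carry-forward wording appears in 2 of 2 cells for A, 2 of 2 for B and 0 of 2 for C. The Cohort C rows match the initial-treatment rows in 8.1. Cohort C was added in Version 2.0 and no reason is given for treating it differently, which suggests carried-over text.

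**2. Size of the literal dose step.** Dose levels are from Table 4 (800, 600, 400 mg).
- Restart at 600 mg: 800 / 600 = 1.33, or +33%.
- Restart at 400 mg: 800 / 400 = 2.00, or +100%. This is two levels, more than even the 8.4.2 exception allows.

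**3. Duration of the literal dose step.**
- Maximum: Cycles 4 to 26 are 23 cycles; 23 x 28 = 644 days.
- Early stop: 7.3 footnote 11 places the first on-treatment MRD test in Cycle 6. Assuming Day 1 of that cycle and confirmation 4 weeks later, exposure covers Cycles 4-6; 3 x 28 = 84 days.

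**4. Synopsis Cohort C re-treatment tables against 8.2 and 7.3 footnote 18.**
- Lead-in missing: 2 x 28 = 56 days.
- Maintenance ublituximab cycles: {9, 12, 15, 18, 21, 24} in the synopsis, {11, 14, 17, 20, 23, 26} in 8.2 and 7.3. Overlap is 0 of 6; each synopsis number plus 2 gives the 8.2 number.
- Ublituximab total under either schedule: 4 + 5 + 6 = 15 infusions; 150 + 750 + 2 x 900 + 11 x 900 = 12,600 mg. Timing differs, amount does not.

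**5. Number of subjects exposed to the 8.2 inconsistency.** The ceiling is the Cohort C enrolment, up to about 28. The documents give neither the share re-treated nor the share of those with an umbralisib reduction. Assuming 20-50% and 10-30%:
- Low: 28 x 0.20 x 0.10 = 0.56.
- High: 28 x 0.50 x 0.30 = 4.2.

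**6. Primary analysis.** Section 11.6.1.1 reports U-MRD at Cycles 3 to 24, the initial-treatment time points. Re-treatment dosing does not enter it.

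**The case against.** The best defence is that 800 mg is a nominal dose. Section 8.1 also prints 800 mg for every cycle of initial treatment, and there it has to be read subject to 8.4, or the Table 3 reductions would mean nothing. On that reading a careful site would never raise a reduced dose, and the +33% or +100% arises only if the dose-modification section is ignored. There are other safeguards: a re-treatment registration form goes to the sponsor (Section 6), and sites are told to raise questions with the sponsor before restarting after long holds (8.4). The synopsis tables are likewise contradicted by the text that introduces them.

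Much of this stands, and it limits the practical consequence. It does not make the tables right. In 8.1 the 800 mg follows a common 800 mg start; in 8.2 Cohort C it follows an individual dose, and the neighbouring cohorts show the intended wording.

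A reader might go further and infer that the Cycle 3 option to start above the last tolerated dose is itself an error in all three cohorts, because it conflicts with 8.4.2. The documents do not show that. The option is printed five times across the synopsis and 8.2, and 7.3 footnote 19 gives the same discretion. Ibrutinib and venetoclax have a parallel option. Re-treatment follows more than 6 months off treatment, so deliberate re-challenge is a plausible intent. Section 8.4.2 does not say whether its bar carries into a new course. That is a question for the sponsor.

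**Conclusion.** Two internal inconsistencies are established, both wrong as written and both confined to Cohort C re-treatment.

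(a) The two umbralisib cells in 8.2 for Cycles 4-8 and 9-26 do not follow from the Cycle 3 cell or match Cohorts A and B. Literally applied, they raise a 600 or 400 mg restart to 800 mg, for between 84 days (early-stop assumption) and 644 days (maximum). Where the earlier reduction was for drug-related toxicity, this also runs against 8.4.2, if that bar carries into re-treatment. The mismatch between cohorts does not depend on that point.

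(b) The synopsis tables omit the 56-day lead-in and place all six maintenance infusions in the wrong cycles.

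The number affected by (a) is small: roughly 0.6 to 4.2 subjects on assumed shares with full Cohort C enrolment, and possibly none. It would be wrong to infer that reduced subjects will in fact be given 800 mg, or that the primary result is at risk. The issue is dosing safety and consistency, and it should be corrected.

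**What to change.** 1. In 8.2, Cohort C re-treatment, Cycles 4-8 and 9-26, replace the umbralisib 800 mg entry with "At appropriate dose based on previous Cycle", as in Cohorts A and B.
2. Replace the synopsis Cohort C re-treatment tables with the corrected 8.2 tables: acalabrutinib alone in Cycles 1-2, triplet in Cycles 3-26.

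Both are wording changes for the next amendment, with no added visit, procedure or subject.

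Separately, ask the sponsor whether the 8.4.2 bar on re-escalation applies across courses, given the Cycle 3 discretion in all cohorts and 7.3 footnote 19. Neither correction above has to wait for the answer.
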